5.1. General Considerations

The following is a list of general reporting conventions:

- Percentages will be based on the number of participants in the analysis set unless otherwise indicated.
- Categorical variables will be summarized using counts (n) and percentages (%) and will be presented in the form of n (%).
- Percentages will be reported to 1 decimal place.
- Continuous data will be summarized using the mean, standard deviation (SD), median, minimum, 25th and 75th percentiles, maximum, and number of participants with data.
- Means and medians will be reported at 1 more significant digit than the precision of the data. Standard deviations and confidence intervals will be reported at 2 more significant digits than the precision of the data. Quartiles, minima and maxima will be reported to the same level of precision as the original observations.
- The median will be reported as the average of the 2 middle numbers if the dataset contains even numbers.
- No preliminary rounding should be performed; rounding should only occur after analysis. To round, consider digit to right of last significant digit: if < 5 , then round down; if ≥ 5 , then round up.
- All p-values will be 1-sided and reported to 3 decimal places (e.g., 0.XXX). Values < 0.001 will be reported as < 0.001 .

If departures from these general conventions are present in the specific evaluations sections of this SAP, then those conventions will take precedence over these general conventions.

5.2. Visit Windows

The following table outlines the analysis visits that data will be mapped to for analysis of efficacy, safety and pharmacodynamics data collected during the study. If after mapping, multiple data points share the same analysis visit, the data point closest to the expected study visit will be used. If there is a tie, the earlier of the visits will be used.

Study Visit	Analysis Visit	Analysis Window
Screening	Screening	0
Baseline	Baseline	0
Days 1 – 9	Days 1 – 9	0

Day 10	Day 10	± 1 day
Day 14	Day 14	± 2 day
Day 21	Day 21	± 3 day
Day 28/EOS	Day 28	± 3 day
Post Study Visit	Day 88	± 10 day

If Baseline is missing then screening data should be mapped to baseline for analysis purposes.

5.3. Missing Data, Outliers, and Pooling

5.3.1. Missing Data

As the rules for imputation of missing data will differ by endpoint, details on imputation rules for missing data are provided with the description of the endpoint and analytical methods for analysis.

5.3.2. Outliers

All reported values will be included in the analyses.

5.3.3. Pooling

Based on the total sample size of the study, and the anticipated number of sites, participants will be pooled across all sites, for all analyses.

5.4. Participant Disposition

A clear accounting of disposition, including the numbers and percentages of participants screened, randomized, completed treatment and completed post treatment follow-up and completed post study follow-up, will be reported overall and by treatment group. In addition, the primary reasons for early discontinuation of study intervention during the treatment period and early study discontinuation will be reported overall and by treatment group. A graphical representation of participant disposition, by treatment group, will be produced using a CONSORT flow diagram.

A summary of the number of participants included in each analysis set (i.e., FAS, MITT, PP, Safety, PK) will be provided overall and by treatment group. Participants could be excluded from an analysis set for more than one reason. All participants excluded from an analysis set will be listed with the reason(s) for exclusion.

A tabular summary of all major protocol violations will be provided by treatment group and overall. Major protocol violations will be classified as follows:

- Violations of inclusion and exclusion criteria
- Receiving the wrong study intervention
- Non-compliance with study intervention. A participant is defined as non-compliant if the participant took < 80% of the study intervention.
- Taking a prohibited medication
- Other

As participants can report multiple protocol violations, they will be included for each observed violation (i.e., these categories will not be mutually exclusive).

5.5. Primary Endpoint(s) Analysis

5.5.1. Definition of Endpoint(s)

Time to Clinical Improvement

Time to clinical improvement will be derived as the earliest date of either not requiring oxygen support or hospital discharge, minus the date of randomization. Participants who die or withdraw from the study prior to observing clinical improvement will be censored on day 28. Participants will be censored on day 28, if clinical improvement has not been observed by this time point. If a participant discontinues study drug early, they will still be assessed for this endpoint until one of the above criteria (i.e., clinical improvement, death/withdrawal, day 28 visit without clinical improvement) is met.

Change from baseline to Day 10 or hospital discharge if sooner, in the ratio of hemoglobin oxygen saturation to inspired oxygen fraction (SpO₂/FiO₂)

SpO₂ and FiO₂ will be collected twice daily while a participant is in hospital. The average of the twice daily SpO₂/FiO₂ ratio will be used for all derivations. If only a single ratio is collected, that single ratio for that day will be used. Once discharged, only a single ratio will be used in the derivations. Participants who are discharged prior to day 10, will have their end of treatment assessment, mapped to day 10.

The SpO₂ value will be recorded on the eCRF. To derive the FiO₂ value, oxygen flow rate as collected on the eCRF will be converted to FiO₂ using the following table.

Method	O2 Flow rate (l/min)	Estimated FiO2 (%)
Nasal cannula	1	24
	2	28
	3	32
	4	36
	5	40
	6	44
Nasopharyngeal catheter	4	40
	5	50
	6	60
Face mask (Simple Mask)	5	40
	6-7	50
	7-8	60
Face mask with reservoir (non-rebreather face mask)	<6	Follow nasal cannula
	6	60
	7	70
	8	80
	9	90
	10	95
	>10	100
Venturi Mask	4	28
	6	31
	8	40
	10	50

The change from baseline to Day 10 or hospital discharge if sooner, in the ratio of hemoglobin oxygen saturation to inspired oxygen fraction (SpO₂/FiO₂) will be derived by taking the SpO₂/FiO₂ ratio at the earlier of day 10 or hospital discharge and subtracting the baseline SpO₂/FiO₂ ratio. Missing data will be assumed to be missing at random and this endpoint will be analyzed using likelihood-based methods, therefore missing data will be maintained as missing.

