1.2. Schedule of Activities (SoA)

Table 2: Schedule of Activities

General Notes:

- In case of natural disasters or pandemics, some visits/study procedures can be done via virtual visits (e.g., telemedicine or telephone) or at home visits after hospital discharge. Refer to study reference manual for more details.
- Assessments completed as part of standard of care within the protocol defined windows, will not need to be repeated specifically for the protocol.

Procedure	Screening	Treatment Period			Follow-up			Post-study visit	Notes
		BL	Daily visits [‡]	EOT/ET*			EOS		
Study Day	-3 to -1	1	2-9	10	14	21	28	+60 days from EOS	Baseline (BL); End of Treatment (EOT), Early termination (ET); End of study (EOS) [‡] If a subject is discharged prior to Day 10, they will complete Day 5 and Day 10 visits assessments * This visit will be conducted at hospital discharge, if subject is discharged prior to Day 10
Visit window (days)				±1	±2	±2	±2	±10	
Informed consent	X								
Inclusion and exclusion criteria	X	X							
Demography	X								
Medical history	X								
Current medical conditions	X	X							Including time from onset of symptoms (fever, cough, etc.) to study entry, COVID-19 severity for each subject
Comprehensive physical exam	X			X					
Height and weight	X			X*					*Weight only

Procedure	Screening	Treatment Period			Follow-up			Post-study visit	Notes
		BL	Daily visits [‡]	EOT/ET*			EOS		
Study Day	-3 to -1	1	2-9	10	14	21	28	+60 days from EOS	Baseline (BL); End of Treatment (EOT), Early termination (ET); End of study (EOS) ‡ If a subject is discharged prior to Day 10, they will complete Day 5 and Day 10 visits assessments * This visit will be conducted at hospital discharge, if subject is discharged prior to Day 10
Visit window (days)				±1	±2	±2	±2	±10	
Limited physical exam		X	Day 5		X	X	X		Physical exam will be symptom-directed exam
Hematology	X	X	Day 5	X	X	X	X		Refer to Section 10.2
Clinical chemistries	X	X	Day 5	X	X	X	X		Refer to Section 10.2
INR	X						X		International normal ratio (INR)
Urinalysis	X						X		Refer to Section 10.2
Sputum samples and nasopharyngeal swab for SARS-CoV-2 PCR		X	Day 5	X	X	X	X		Samples to be frozen as specified in the laboratory manual for viral quantification.
Serum hsCRP and ferritin		X	Day 5	X	X	X	X		High sensitivity c-reactive protein (CRP)
Reserve blood sample for biomarker analyses		X	Day 5	X	X	X	X		Date and times to be recorded when samples were collected.
IL-6		X	X	X	X	X	X		Interleukin 6 (IL-6)

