Hospital discharge readiness assessment		X	X	X	X	X	X		Refer to Section 8.1.5
Clinical status 6-point ordinal scale	X	X	X	X	X	X	X		Refer to Section 8.1.2
State of consciousness	X	X	X	X	X	X	X		Level of consciousness: alert (A), arousable only to voice (V), or pain (P) and unresponsive (U)

Procedure	Screening	Treatment Period			Follow-up			Post-study visit	Notes
		BL	Daily visits [‡]	EOT/ET*			EOS		
Study Day	-3 to -1	1	2-9	10	14	21	28	+60 days from EOS	Baseline (BL); End of Treatment (EOT), Early termination (ET); End of study (EOS) [‡] If a subject is discharged prior to Day 10, they will complete Day 5 and Day 10 visits assessments * This visit will be conducted at hospital discharge, if subject is discharged prior to Day 10
Visit window (days)				±1	±2	±2	±2	±10	
Randomization		X							
Study drug administration		X	X	X					Treatment to be administered during hospitalization only
Study drug accountability			X	X					
AE and SAE review		X	X	X	X	X	X		Adverse event (AEs), Serious AE (SAEs)
Prior and concomitant medication	X	X	X	X	X	X	X		
Survival status					X	X	X	X	

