7.2. Discontinuation of Study Drug

In some instances, it may be necessary for a subject to permanently discontinue study drug. Please also refer to stopping rules described in [Section 7.1](#).

Permanent discontinuation of study drug does not mean withdrawal from the study, and the subject will be encouraged to remain in the study and continue to complete all study visits. See the SoA ([Section 1.2](#)) for data to be collected at the time of drug discontinuation and follow-up and for any further evaluations that need to be completed.

Subjects may discontinue or be discontinued from study drug at any time. A subject may discontinue study drug for reasons including but not limited to:

- Adverse event
- Death
- Lost to follow-up
- Non-compliance with study drug
- Physician decision
- Pregnancy
- Lack of efficacy
- Protocol deviation
- Study terminated by Sponsor
- Withdrawal by subject* (*only for discontinuing study drug, but will remain in study)

The reason for subject discontinuation from study drug will be recorded in the eCRF. At the time of treatment completion or study drug discontinuation, the EOT/ET visit should be completed as shown in the SoA ([Section 1.2](#)). Subjects should continue to be followed for safety even if they discontinue study drug prematurely unless they withdraw consent.

Pregnancy is a mandatory criterion for permanent discontinuation of study drug (see [Section 7.1.1](#)).

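### SAP and protocol give conflicting Day 10/Discharge SpO2/FiO2 values for a participant who stops study drug in hospital and is discharged before Day 10

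*SAP*

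**What the plan says.** Five pieces of text decide which value is used.

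- **Mapping, SAP 5.5.1:** "Participants who are discharged prior to day 10, will have their end of treatment assessment, mapped to day 10".
- **Derivation, SAP 5.5.1, a few lines later:** the change is formed by taking the "ratio at the earlier of day 10 or hospital discharge and subtracting the baseline" value. SAP 5.5.2 labels the MMRM time point Day 10/Discharge and reads the treatment contrast there.
- **Visit timing, Protocol 7.2:** "At the time of treatment completion or study drug discontinuation, the EOT/ET visit should be completed as shown in the SoA". The same section says "Permanent discontinuation of study drug does not mean withdrawal from the study", so drug-stoppers stay under observation.
- **Visit timing, Protocol 1.2, footnote to the EOT/ET column:** "This visit will be conducted at hospital discharge, if subject is discharged prior to Day 10". A second footnote there says: "If a subject is discharged prior to Day 10, they will complete Day 5 and Day 10 visits assessments".
- **Competing values, SAP 5.2:** "If after mapping, multiple data points share the same analysis visit, the data point closest to the expected study visit will be used". The Day 10 window is ±1 day, and a tie goes to the earlier value.

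The Schedule of Activities has a single EOT/ET column for both triggers.

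**The concern.** The mapping sentence works only if the end-of-treatment assessment and the discharge assessment are the same visit. For most participants discharged early they are, because the Schedule of Activities says of dosing: "Treatment to be administered during hospitalization only". Someone who finishes dosing by leaving hospital has both on one day.

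They separate for a participant whose drug is stopped in hospital some days before an early discharge. Protocol 7.2 then calls for the EOT/ET visit at the stop, and that reading may be taken while the participant still needs oxygen. If it fills the Day 10 slot, one of the two primary endpoints uses a mid-illness reading where its definition asks for the reading at discharge. If such stopping is more common in one arm, the treatment difference at that time point is biased.

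**Working it through.** **Step 1. Apply the texts to one case.** Suppose drug is stopped on Day 3 while the participant is on oxygen, and discharge on room air follows on Day 8.

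| Text applied | Value in the Day 10/Discharge slot |
|---|---|
| SAP 5.5.1 mapping + Protocol 7.2 | Day 3 |
| SAP 5.5.1 mapping + Schedule of Activities footnote | Day 8 |
| SAP 5.5.1 derivation, SAP 5.5.2 | Day 8 |
| Post-discharge Day 10 visit + SAP 5.2 closest-value rule | About Day 10 |

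SAP Section 1 lets the SAP prevail over the protocol. That does not settle the matter: the SAP never says when the end-of-treatment assessment takes place, and its own sentences lead to different values. The default MMRM time points are Days 1 to 5 and Day 10/Discharge, with Days 6 to 9 optional. On the first reading, unless the optional days are added, the Day 3 ratio enters twice and the Day 8 ratio not at all.

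**Step 2. Reproduce the plan's power.** Inputs from SAP Section 3: difference 25, SD 40, 80 active and 40 control, two-sided 5%.

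SE = 40 × √(1/80 + 1/40) = 7.746. Power = Φ(25/7.746 − 1.96) = Φ(1.267) = 89.8%. A noncentral t with 118 df gives 89.3%. The stated figure of approximately 90% stands.

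**Step 3. Show what the drug-stop reading could do.** The documents give neither the share of participants affected nor the gap between the two readings, so everything here is assumed. Let fa and fc be the shares affected in the active and control arms, and s the discharge ratio minus the drug-stop ratio.

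Observed difference = 25 − (fa − fc) × s, with the SD held at 40. Cells show the difference and the power.

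| fa | fc | s = 25 | s = 50 | s = 100 |
|---|---|---|---|---|
| 5% | 5% | 25.0 (89.8%) | 25.0 (89.8%) | 25.0 (89.8%) |
| 5% | 0 | 23.75 (86.6%) | 22.5 (82.8%) | 20.0 (73.3%) |
| 10% | 5% | 23.75 (86.6%) | 22.5 (82.8%) | 20.0 (73.3%) |
| 10% | 0 | 22.5 (82.8%) | 20.0 (73.3%) | 15.0 (49.1%) |
| 0 | 5% | 26.25 (92.3%) | 27.5 (94.4%) | 30.0 (97.2%) |

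**Step 4. Ask how large s could be.** Assume SpO2 94% on nasal cannula at 3 L/min at the stop (FiO2 32% in the SAP table) and SpO2 96% on room air at discharge (FiO2 21%, an assumption, since the table has no room-air row).

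94/0.32 = 293.8; 96/0.21 = 457.1; s ≈ 163. At 2 L/min, 457.1 − 94/0.28 = 121. At 5 L/min, 457.1 − 94/0.40 = 222.

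With s = 163.4 and 2, 4 or 8 of the 80 active participants affected and no controls, the difference falls by k × 163.4/80 = 4.1, 8.2 or 16.3 points, and power falls to about 77%, 58% or 20%. With 5% affected in both arms the difference is unchanged, but the SD rises to about √(40² + 0.05 × 0.95 × 163.4²) = 53.6, and power falls to about 67%.

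**The case against.** The best defence is that the documents mostly point to discharge. Protocol 7.2 defers to the Schedule of Activities, whose footnote places the visit at discharge for exactly the group the mapping sentence covers. The endpoint, the second hypothesis, the derivation sentence and the MMRM time point all name discharge. This stands as evidence of intent. It does not remove the drug-stop trigger in 7.2, and a programmer working from the mapping sentence would look for the EOT/ET record.

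A reader might infer that drug-stoppers *are* scored on the stopping day. The documents do not support that. Besides the footnote, a post-discharge Day 10 value would displace a Day 3 value under SAP 5.2.

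A reader might also infer that all recovery after stopping is thrown away. It is not: in the example the Day 4 and Day 5 ratios stay in the model, and SAP 5.5.1 keeps assessing drug-stoppers for time to clinical improvement.

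Nor do the documents show that stopping will differ by arm. Protocol 7.2 lists adverse events among the reasons for stopping, and Appendix 5 provides for withholding or discontinuing drug after troponin elevation. But Protocol 4.3 reports good tolerability in earlier dosing, and Protocol 2.3.1 says the Phase 1 troponin rises resolved while dosing continued.

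The mapping sentence recurs for calprotectin, the 6-point scale, viral load, IL-6 and D-dimer. The case is weaker there, because the SAP labels their Day 10 time point Day 10/EOT.

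**Conclusion.** The conflict is real and the plan does not resolve it. For a participant who stops drug in hospital and leaves before Day 10, three different readings can claim the Day 10/Discharge slot of a primary endpoint. One of them, the drug-stop reading, contradicts the endpoint's own definition.

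The drug-stop problem is confined to that narrow subgroup. The choice between the discharge reading and a later Day 10 reading arises for anyone discharged early.

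Size and direction cannot be set from the documents. With equal shares affected and equal gaps, the difference does not move, though noise may rise. More stopping in the active arm shrinks the difference, and more in control inflates it. The figures above rest on assumed shares, oxygen flows and saturations, and apply only if the drug-stop value is in fact used. The sample-size calculation is not in error. The point is worth correcting because it concerns a primary endpoint and the remedy is nearly free.

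**What to change.** 1. In SAP 5.5.1, replace the reference to the end-of-treatment assessment with the SpO2/FiO2 ratio on the day of hospital discharge, using the section's existing averaging rule.
2. State that this value takes precedence over a later post-discharge Day 10 value and over an earlier EOT/ET visit triggered by stopping drug. Analyse that earlier visit at its actual study day.
3. Reconcile Protocol 7.2 with the Schedule of Activities footnote on when the EOT/ET visit takes place.
4. For calprotectin, the 6-point scale, viral load, IL-6 and D-dimer (SAP 5.6.1, 5.6.2, 5.7, 5.9.2), state separately that the Day 10 slot uses that endpoint's own discharge-visit assessment where one exists, not a drug-stop visit. The oxygen-ratio wording should not be copied into those sections.

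The cost is a few sentences and a programming rule. In-hospital SpO2 and FiO2 are already recorded twice daily, so the primary endpoint needs no new data. SAP 5.10 says enrolment had completed, so adding a separately labelled visit to the schedule would do little for this cohort. The rule should be settled before the arms are compared, including at the pre-lock interim described in SAP 5.10.

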5.5.2. Main Analytical Approach

Time to Clinical Improvement

Time to clinical improvement will be presented by treatment group, using the Kaplan-Meier estimator. A Cox proportional hazards model with treatment, remdesivir strata (yes/no) and age (years) as covariates will be used to estimate the hazard ratio and compare treatment groups. Additional covariate's (i.e., Country (USA, Brazil), Chloroquine or hydroxychloroquine use (yes vs no), HIV anti-viral drug use (yes vs no), corticosteroid use (yes vs no) and azithromycin use (yes vs no)) may also be included if these are found to influence the treatment effect, based on observing p-value of < 0.05 for the covariate, after adjusting for the others in the model. The

stepwise selection procedure will be used to assess the additional covariates. In addition, the log rank test and stratified log rank test, with remdesivir as the strata, will be provided. The primary analysis will be conducted using the FAS.

Change from baseline to Day 10 or hospital discharge if sooner, in the ratio of hemoglobin oxygen saturation to inspired oxygen fraction (SpO₂/FiO₂)

The primary efficacy endpoint of change from baseline to Day 10 or hospital discharge if sooner, in the ratio of hemoglobin oxygen saturation to inspired oxygen fraction (SpO₂/FiO₂) will be analyzed using a mixed model for repeated measures (MMRM). The Kenward-Roger method will be used to calculate the denominator degrees of freedom for the test of fixed effects and adjusted standard errors. The model will contain treatment, time and the treatment by time interaction as fixed effects and baseline score, age (years), corticosteroid use (yes vs no) and remdesivir strata as covariates. If age and/or corticosteroid use are not significant at the 5% level, they will be removed from the model. As the follow-up visit schedule for each participant will be variable, the following timepoints will be used; Day 1, Day 2, Day 3, Day 4, Day 5 and Day 10/Discharge. Additional time points (e.g., Days 6-9) may be included if most participants are not discharged prior to Day 10. An unstructured covariance matrix will be assumed to model the within-participant errors. This variance-covariance matrix will be estimated across treatment groups. However, if there is a convergence problem with the unstructured covariance matrix, then alternative covariance structures will be examined (heterogeneous Toeplitz structure, Compound Symmetry) and the one with the best fit as determined by the Akaike information criteria (AIC) (i.e., smallest AIC value) will be used. The least squares means (LS-means) for each treatment, LS-means treatment difference and corresponding confidence interval (CI) for the LS-means difference and p-value for the treatment difference, will be reported at the Day10/Discharge timepoint.

The primary analysis will be conducted using the FAS.

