5. STUDY POPULATION

5.1. Eligibility Criteria

5.1.1. Inclusion Criteria

To be eligible for participation in this study, subjects must meet all the following:

Age

1. At least 18 years of age at the time of signing the ICF.

Type of Subject and Disease Characteristics

2. Hospitalized for COVID-19.
3. Diagnosed with COVID-19 as defined by having at least 2 of the following signs or symptoms within the past 2 days:
 - a. Fever defined as a body temperature of ≥ 38.0 °C oral, or ≥ 38.3 °C rectal, ≥ 37.7 °C forehead or ≥ 38.7 °C aural (axillary temperatures are not allowable);
 - b. Cough;
 - c. Fatigue;
 - d. Shortness of breath.
4. Radiographic evidence (chest x-ray or CT scan) of one the following:
 - a. Ground-glass opacities, or
 - b. Local or bilateral patchy infiltrates, or
 - c. Interstitial pulmonary infiltrates.
5. Oxygen requirements:
 - a. $SpO_2 \leq 94\%$ on ambient airOR
 - b. Requires supplemental oxygen administration by nasal cannula, simple face mask, or other similar oxygen delivery device.

Sex

6. Male and/or female subjects.

Contraception use by men or women should be consistent with local regulations regarding the methods of contraception for those participating in clinical studies.

7. All subjects (male or female) who are of childbearing potential must agree to use highly effective contraception during the study. Female subjects and male partners of female subjects must continue to use highly effective contraception for 30 days after the last dose of study drug. Female subjects should not donate oocytes during this time. Male subjects and female partners of male subjects must continue to use highly effective contraception for 90 days. Male subjects must agree not to donate sperm during this time.

Note: Abstinence is acceptable if this is the usual lifestyle and preferred contraception for the subject.

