6.4. Measures to Minimize Bias: Randomization and Blinding

All subjects will be centrally assigned to randomized study drug using an Interactive Response Technology (IRT). Before the study is initiated, the log in information & directions for the IRT will be provided to each site.

Randomization will be stratified by remdesivir use at study entry (yes/no)

Study drug will be dispensed by the unblinded pharmacy staff to the study staff/research nurse in a blinded manner per the schedule summarized in the SoA ([Section 1.2](#)).

The IRT will be programmed with blind-breaking instructions. Subject safety must always be the first consideration in making such a determination. If the Investigator decides that unblinding is warranted, the Investigator should make every effort to contact the Sponsor prior to unblinding a subject's drug assignment unless this could delay emergency treatment of the subject. If a subject's drug assignment is unblinded, the Sponsor must be notified within 24 hours after breaking the blind. The date and reason that the blind was broken must be recorded in the source documentation and case report form, as applicable.

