Assuming the median time to clinical improvement, defined as no longer requiring oxygen support or hospital discharge whichever occurs first, will be 12-15 days in the placebo group, and that at least 75 of the planned 120 participants enrolled meet the clinically improved criteria, the study will have at least 80% power to detect a 50% reduction in the time to clinical improvement, (i.e., hazard ratio[BLD2660/Placebo] of 0.5) with a two-sided 5% significance level.

The total number of events (d) is estimated based on the following formula

$$d = \frac{(z_{\alpha/2} + z_{\beta})^2}{\pi(1 - \pi)\theta^2}$$

where $z_{\alpha/2}$ and z_{β} are the value from a standard normal distribution, π is the proportion of participants randomized to control, $1 - \pi$ is the proportion of participants randomized to active and θ is the inverse of the log hazard ratio, as we are modeling improvement. The total number of participants is then calculated as the number of events divided by the probability of observing the event during the study. For this study $\alpha = 5\%$, $\beta = 20\%$, $\pi = 1/3$ and $\theta = 1/\log(0.5)$ and the probability of observing an event is 0.60.

Change from baseline to Day 10 or hospital discharge if sooner in the ratio of hemoglobin oxygen saturation to inspired oxygen fraction (SpO₂/FiO₂).

A prospective observational cohort study of non-intubated moderate to severe ARDS participants (Ding, 2020) reported the partial pressure of oxygen (PaO₂)/FiO₂ ratio for 10 participants, which gave a mean and standard deviation of 147 ± 46 mm Hg. Converting to a SpO₂/FiO₂ ratio gives a mean and standard deviation of 192 ± 39 using the equation reported by Rice et al. (2007) (Rice, 2007).

Assuming a standard deviation of 40 in the SpO₂/FiO₂ ratio, a sample size of 120 participants (80 active, vs 40 control) will provide approximately 90% power to detect a treatment difference in the SpO₂/FiO₂ ratio of 25 or greater, based on a two-sample t-test with a two-sided 5% significance level.

CONFIDENTIAL

Statistical Analysis Plan [Version 3.0]

The total number of participants (N) is estimated based on the following formula

$$N = \frac{(z_{\alpha/2} + z_{\beta})^2}{\pi(1 - \pi)\theta^2}$$

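### The Cox model for time to clinical improvement has no baseline oxygen-severity covariate: the test stays valid, but the hazard ratio is attenuated, power is lost, and the estimate is exposed to chance imbalance at 80 versus 40

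*SAP*

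**What the plan says.** **Who can enter.** Protocol 5.1.1 (inclusion 5) admits subjects with SpO2 of 94% or less on ambient air, or a subject who "Requires supplemental oxygen administration by nasal cannula, simple face mask, or other similar oxygen delivery device". Protocol 5.1.2 excludes those needing FiO2 of 0.75 or more (exclusion 5) and those requiring or expected to require mechanical ventilation (exclusion 9).

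**Randomization.** Protocol 6.4: "Randomization will be stratified by remdesivir use at study entry (yes/no"). There is no other factor. Allocation is 2:1, 80 active and 40 control.

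**Time to clinical improvement (SAP 5.5.2).** "A Cox proportional hazards model with treatment, remdesivir strata (yes/no) and age (years) as covariates will be used to estimate the hazard ratio". Country, chloroquine or hydroxychloroquine, HIV antivirals, corticosteroids and azithromycin can enter by stepwise selection. The log-rank tests are unstratified or stratified by remdesivir. The only sensitivity analysis is the per-protocol set (5.5.3), there are no supplementary analyses (5.5.4), and no subgroup is defined by baseline oxygen need (5.9.3).

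**The other primary endpoint (SAP 5.5.2).** "The model will contain treatment, time and the treatment by time interaction as fixed effects and baseline score, age (years") and further terms. Here the baseline SpO2/FiO2 is in the model.

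**What is collected.** The Schedule of Activities (protocol 1.2) has SpO2, FiO2 and the 6-point score at screening and Day 1, and APACHE II on Day 1. The current-conditions entry carries the note "Including time from onset of symptoms (fever, cough, etc.) to study entry, COVID-19 severity for each subject".

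**The concern.** The event is coming off oxygen or leaving hospital, so the oxygen support a subject needs at entry is the starting distance from the event. It is the most obvious prognostic variable for this endpoint, and the sponsor already adjusts for it in the other primary model. In the Cox model it is neither fixed nor a candidate. Hydroxychloroquine use is a candidate although treatment with it at entry is excluded (exclusion 10), so that variable can only reflect use begun later.

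Two things are at stake. Leaving a strong prognostic factor out of a Cox model moves the treatment hazard ratio toward 1 even when the arms are balanced. And with 40 controls, a moderate chance imbalance in severity passes straight into the estimate. Either primary endpoint alone can declare success (SAP 2), and SAP 5.10 plans an interim to support Phase 3 planning, so a diluted or shifted hazard ratio could mislead that decision.

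**Working it through.** **1. The plan's own figure.** SAP 3 claims that "the study will have at least 80% power to detect a 50% reduction in the time to clinical improvement", "with a two-sided 5% significance level", with 75 events among 120. SAP 5.1 adds: "All p-values will be 1-sided and reported to 3 decimal places". The one-sided 2.5% level in SAP 5.10 has the same critical value, 1.96.

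- Events = (1.96 + 0.842)² / [(1/3)(2/3)(ln 0.5)²] = 7.849 / 0.1068 = 73.5, so 74.
- Power at 75 events = Φ(√(75 × 2/9) × 0.693 − 1.96) = Φ(0.87) = 80.8%.

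The stated figure reproduces. The formula has no term for prognostic heterogeneity.

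**2. Events by day 28.** With exponential times and recovery hazard ratio 2.0 (the inverse of the SAP's 0.5):

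- Placebo median 12 days: 40 × (1 − 0.5^(28/12)) + 80 × (1 − 0.5^(56/12)) = 40 × 0.802 + 80 × 0.961 = 108.9.
- Placebo median 15 days: 40 × 0.726 + 80 × 0.925 = 103.0.

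Follow-up to day 28 therefore gives more than 75 events, which is why the simulated powers below start near 91% rather than 80%.

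**3. Simulation.** Inputs from the plan: 80 versus 40, recovery hazard ratio 2.0, control median 13.5 days (middle of 12–15), censoring at day 28, one-sided 2.5%. Assumed: exponential times and the prognostic strength of severity. The comparison is Cox with treatment alone against Cox with treatment plus severity.

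| Severity assumption | HR without | HR with | Power without | Power with |
|---|---|---|---|---|
| Not prognostic | 2.01 | 2.02 | 91% | 91% |
| Three levels (35/35/30%), 1.5-fold per step | 1.92 | 2.03 | 87% | 91% |
| Three levels (35/35/30%), 2-fold per step | 1.79 | 2.03 | 76% | 88% |
| Normal score, 1.5-fold per SD | 1.88 | 2.02 | 84% | 90% |
| Normal score, 2-fold per SD | 1.73 | 2.01 | 71% | 88% |
| Normal score, 3-fold per SD | 1.56 | 1.99 | 50% | 85% |

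To put the rows on one scale: the three-level score has variance 0.35 × 0.95² + 0.35 × 0.05² + 0.30 × 1.05² = 0.6475, SD 0.805. So 1.5-fold per step is 1.5^0.805 = 1.39 per SD, and 2-fold per step is 2^0.805 = 1.75 per SD. A repeat of the three-level rows with 1,500 trials gave 85% against 89% and 75% against 87%, so read them to about two points.

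**4. Type I error.** With no drug effect and 1.5-, 2- or 3-fold per SD, one-sided rejection without severity was 1.7–2.1% (6,000 trials each, cut at 75 events). It is not above 2.5%.

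**5. Chance imbalance.** Ignoring the remdesivir stratification, the standard error of the standardized difference in baseline severity is √(1/80 + 1/40) = 0.194. An absolute difference above 0.2 has probability 30%, above 0.3 12%, and above 0.4 4%. A difference of 0.3 SD moves the unadjusted hazard ratio by about 1.5^0.3 = 1.13, 2^0.3 = 1.23 or 3^0.3 = 1.39.

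**The case against.** A reader might infer that disease course is confounded with treatment, so that the trial partly measures who was sicker at entry. The documents do not support that. Randomization balances severity in expectation, type I error is not inflated, and attenuation toward 1 is conservative. Figures restricted to badly imbalanced trials describe a selected subset, not the plan's operating characteristics.

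Other points on that side stand in part:

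- At the milder assumption (1.5-fold per step), power stays above the 80% target without adjustment. The loss rests wholly on an assumed prognostic strength.
- The simulated comparator is treatment alone. The planned model has remdesivir stratum and age, which the protocol's background links to severe disease and serious outcomes. They may act as partial proxies, although a remdesivir-like proxy recovered only 0–3 points in a check.
- Severity was simulated without error. SAP 5.5.1 derives FiO2 from flow rate where needed, so the real gain may be smaller.
- Exclusion 9 narrows the severe end of eligibility.
- The schedule puts baseline measures on Day 1 without saying they precede dosing, and SAP 5.5.1 averages the two daily ratios, so a Day 1 value may include a post-dose reading.
- Only one of two primary endpoints is affected, in a Phase 2 trial.

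None of this removes the omission, and the plan gives no reason for treating the two primary models differently.

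**Conclusion.** The omission is real and worth correcting, as a matter of efficiency and precision rather than validity. At the plan's own effect the loss is about 4 points of power at 1.5-fold per step (91 − 87) and 12 points at 2-fold (88 − 76), with the hazard ratio falling from 2.03 to 1.92 or 1.79. If severity is not prognostic, adjusting costs essentially nothing. These sizes assume exponential recovery, the three-level severity mix and an error-free covariate, and they do not test the planned model with remdesivir and age.

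Two further inferences go beyond this point. Eligibility sets no maximum time since symptom onset, but nothing here quantifies what adjusting for it would gain. Also, a subject who enters on ambient air may already count as not requiring oxygen support. That is a separate endpoint-definition issue, and a covariate does not repair it.

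**What to change.** In the Cox model of SAP 5.5.2, add the last pre-dose SpO2/FiO2 as a fixed covariate that is always included and not subject to stepwise selection. Use the screening value where no Day 1 pre-dose value exists. Time to discharge readiness (SAP 5.6.2) follows the same approach and would inherit it. Days from symptom onset is optional.

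SAP 1 requires a protocol amendment for a change to a primary analysis, so this is more than a wording edit. It should be dated before the sponsor sees any treatment-level results, including the Phase 3 planning interim in SAP 5.10, and should state that the DMC has already reviewed efficacy data. If that point has passed, keep the current primary model and add the adjusted model to SAP 5.5.3 as a labelled sensitivity analysis.

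The cost is one degree of freedom and the amendment. The measurements are already scheduled, but their timing relative to the first dose must be confirmed. Stratifying randomization by severity is no longer possible, because enrolment is complete (SAP 5.10).
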